### 12.8.4 Subgroup Analyses

The primary and all secondary efficacy endpoints will be summarized descriptively in each baseline PGA subgroup, study center, age (<65, >=65), sex, race (White, Other), duration of disease (<5 Years, 5-10 Years, >10 Years), %BSA affected (<10%, >=10%) and country (USA and Canada). The %BSA Affected continuous outcome will be further explored with summaries of change and % change in %BSA Affected at Week 12 by body region. The implications of any significant heterogeneity on the assessment of overall efficacy will be explored.

### 12.9 Safety Analysis

All safety analyses will be conducted in the Safety Population. Data will be listed by subject and treatment and summarized by treatment. No formal statistical comparisons will be made for safety data.

Single 12-lead ECGs, Hospital Anxiety and Depression Scale (HADS) collected at Screening visit will be presented in a by-subject listing.

#### 12.9.1 Adverse Events

AE terms will be coded using the MedDRA dictionary. A treatment-emergent AE (TEAE) is defined as an AE that starts after the first dose of study medication. For subjects not rolling over to Open-label study, all reported AEs will be included in the Double-Blind phase summaries. For subjects rolling over to the Open-label study, all AEs with an onset date on or before the Week 12 visit date will be included in the Double-Blind phase summaries.

If relationship to treatment is missing, the event will be conservatively treated as related to study drug. Missing severity will be imputed to the highest severity level (most severe).

All AEs will be listed by treatment and by subject, detailing the verbatim term given by the investigator, the preferred term (PT), system organ class (SOC), onset date and time, end date and time, duration (days), CTCAE grade, outcome, relationship to study drug/treatment, action taken with study drug/treatment, other action taken to treat the event, seriousness and criteria for seriousness. Serious AEs (SAEs), TEAEs leading to study discontinuation, TEAEs related to study drug will also be listed separately. The following adverse event of special interest (AESIs) will be identified and listed separately: contact dermatitis, folliculitis, and headache.

AEs will be summarized by treatment and overall as incidence rates of:

- Any AE
- Any TEAE
- Any AESIs
- Any treatment-related TEAE, including definitely, probably, and possibly related
- Any TEAE leading to study drug discontinuation
- Any SAE (non-Fatal)
- Any serious TEAE
- Death
- Treatment-related Serious TEAE
- Serious TEAE leading to study drug discontinuation

Individual PTs will be summarized by treatment according to the following:

- All TEAEs by SOC in alphabetical order and PT in descending order of combined frequency (also for treatment-related TEAEs, TEAEs leading to study discontinuation and serious TEAEs)
- All TEAEs by SOC, PT, and maximum CTCAE grade
- All TEAEs by SOC, PT, and maximum causality (not related, related) to the study drug

In addition, TEAEs and serious TEAEs will be summarized by SOC (alphabetical order) and PT (descending order) for the following subgroups:

- Age (<65 and >=65 years old)
- Sex
- Race (White, Other)

At each level of summarization, a subject will be counted once if he/she reported one or more events. The severity of TEAEs and relationship to study drug will be summarized in a similar manner. For summaries of relationship to study drug, a subject will be classified according to the closest relationship. For summaries of TEAE CTCAE grade, a subject will be classified according to the worst grade.

For AESIs, summarization will be more extensive, reflecting the more detailed information collected. Information summarized will include number of events per subject, earliest onset day, duration (in days), causality, grade and seriousness of AESIs, outcome, actions taken with study drug, assorted physical characteristics of the AESIs, and demographic/baseline characteristics and PGA status of the subjects experiencing them. Each type of AESI will be summarized separately. If a subject has more than one treatment-emergent occurrence of an AESI, the subject's maximum duration, highest levels of causality and seriousness, maximum grade and generally the most extreme level of each characteristic will be summarized. If an AESI was ongoing at EOS, it will not be included in the duration summary.

A Kaplan-Meier figure will be generated for each AESI of time to first event. Subjects not experiencing the AESI will be censored at the date of study completion or discontinuation.

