## 8.3. Time Period and Frequency for Event Assessment and Follow-Up

#### **8.3.1.** Adverse Event Reporting

All AEs will be collected from the time of signed informed consent until the final visit.

Any AEs assessed as related to study participation (eg, protocol-mandated procedures, invasive tests, or change in existing therapy) will be collected from the time a subject consented to participate in the study up to and including any follow-up contact.

All SAEs will be recorded in the eCRF and reported to the Sponsor within 24 hours via email or phone (refer to Medical Monitor/Sponsor Information page for contact information) (see Section 8.4).

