#### 10.4.3. Safety Analyses

The Safety Population will be used in the analysis of safety data. Data will be listed by subject and treatment and summarized by treatment. No formal statistical comparisons will be made for safety data.

The number and proportion of subjects with TEAEs will be summarized by treatment, system organ class, and preferred term for all TEAEs, all TEAEs considered by the Investigator to be related to study drug, all SAEs, and all TEAEs leading to study drug discontinuation. Summaries of AEs will be presented separately for double-blind and open-label treatment phases. All AE summaries will include information for AEs that occurred after administration of the first dose of study drug until completion of the final study visit. Data listings will be provided for subjects who discontinued the study due to an AE and for subjects with an SAE.

Selected laboratory data will be analyzed using descriptive summary statistics and will be presented by study visit and treatment group, including the number of non-missing observations, mean and SD, median, upper and lower quartiles, minimum and maximum for values and changes from Baseline. Categorical safety data will be analyzed using frequency tables and, if applicable, shift tables.

Vital signs will be listed by subject and summarized by visit.

Mean scores from the LTS will be summarized by visit.

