### 3. STUDY DESIGN

This is a double-blind, randomized, vehicle-controlled, Phase 3, multicenter study to evaluate the efficacy and safety of topical tapinarof cream, 1% compared with vehicle-control cream in adults with plaque psoriasis.

Following a 34-day screening period, eligible subjects will be randomized at a 2:1 ratio to receive once daily treatment with tapinarof cream, 1% or vehicle cream. Subjects will return to the clinic at Weeks 2, 4, 8, and 12 for efficacy and safety assessments. Additionally, subjects will be contacted by phone at Weeks 6 and 10 to assess adverse events (AEs) and concomitant medications, to review study drug administration instructions, and to confirm subject's continued participation in this study. Study drug will be dispensed to subjects during the clinic visits and will be administered at home between clinic visits as instructed by site personnel. Subjects will

be instructed to apply study drug once daily to all affected areas, including newly appearing lesions and lesions/areas that improve during the study. Subjects will apply sufficient study drug to cover completely each lesion with a thin layer of study drug and will record the time of study drug application in a daily diary provided by the study site. (Note that subjects are allowed, but not required, to treat fingernails, toenails, palms, soles, and scalp lesions with study drug; however, efficacy analyses will not include assessment of improvement of psoriasis in these areas.) Subjects will be instructed to maintain the dosing time chosen at the beginning of the study for their full study participation. At the phone contacts at Weeks 6, 10, and 14, subjects should be reminded to complete their daily diary and bring it with them to the next clinic visit.

At the end of 12 weeks of treatment in this study, subjects will have the option to enroll in a separate open-label long-term safety and efficacy study for an additional 40 weeks of treatment. Subjects who choose not to participate in the open-label long-term study, who fail to qualify for participation in the open-label long-term study, or who qualify to participate in the open-label long-term study but ultimately elect not to enroll in that study, will complete a Follow-up Visit approximately 4 weeks (Week 16 visit) after the end of treatment in this study. Subjects who withdraw from the study before Week 12 will complete an Early Termination Visit.

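### Adverse events are counted to Week 12 for subjects who roll over and to last report for everyone else, so crude TEAE percentages can be modestly distorted if rollover or withdrawal differs by arm

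*SAP*

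**What the plan says.** SAP 12.9.1 gives a TEAE a lower time bound only: "A treatment-emergent AE (TEAE) is defined as an AE that starts after the first dose of study medication". What enters the double-blind tables then depends on what the subject does at the end of treatment.

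- Not rolling over: "For subjects not rolling over to Open-label study, all reported AEs will be included in the Double-Blind phase summaries".
- Rolling over: "all AEs with an onset date on or before the Week 12 visit date will be included in the Double-Blind phase summaries".

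SAP 3 says that completers who do not enter the open-label study "will complete a Follow-up Visit approximately 4 weeks (Week 16 visit) after the end of treatment in this study". Protocol 7.4 records adverse events at that visit. Study drug is collected at Week 12 (Protocol 7.3.4), so the extra weeks are off treatment.

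Early withdrawers also fall under not rolling over. SAP 3 says of them: "Subjects who withdraw from the study before Week 12 will complete an Early Termination Visit". Footnote a to the Schedule of Assessments lists the Follow-Up Visit for them as well. These passages need to be reconciled, because they decide how long a withdrawer is observed.

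Incidence is tabulated by treatment, each subject counting once however many events occur. No exposure-adjusted rate, common-window table or on-treatment-only table is planned. SAP 12.9 plans no formal tests on safety data.

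**The concern.** A subject's counting window depends on something that happens after randomisation. Subjects may decline the open-label study, fail to qualify, or qualify and not enrol. Response and tolerability could plausibly influence this, and nothing in the design forces balance between arms. A crude percentage rises with time observed. If one arm has more non-rollover completers, its percentage gains events from weeks off drug. If one arm has more early withdrawers, its percentage loses events that would have been seen later.

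At stake is how the TEAE tables are read. With no formal safety comparison planned, these percentages are the main safety evidence by arm, and they would not all refer to the same length of time or to time on drug.

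**Working it through.** The plan states no TEAE rate and no rollover rate, so there is no figure of its own to reproduce. What follows is an illustration with assumed rates.

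**Window length for completers.** Week 12 is Day 85 and Week 16 is Day 113 (Schedule of Assessments). The difference is 113 − 85 = 28 days, so 16 weeks against 12, a window one third longer.

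**Assumptions.** True 12-week incidence I12 = 40% in both arms; constant hazard, the same on and off drug; everyone completes 12 weeks; a share r of each arm rolls over.

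- Weekly hazard: h = −ln(1 − 0.40)/12 = 0.0426.
- 16-week incidence: I16 = 1 − 0.60^(16/12) = 49.4%.
- Crude incidence in an arm: r × I12 + (1 − r) × I16.
- At r = 0.9: 0.9 × 40 + 0.1 × 49.4 = 40.9%.
- At r = 0.8: 0.8 × 40 + 0.2 × 49.4 = 41.9%.

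| Rollover, tapinarof / vehicle | Crude incidence | Spurious difference, points |
|---|---|---|
| 90% / 90% | 40.9% / 40.9% | 0 |
| 90% / 80% | 40.9% / 41.9% | −0.9 |
| 90% / 70% | 40.9% / 42.8% | −1.9 |
| 90% / 60% | 40.9% / 43.8% | −2.8 |
| 90% / 50% | 40.9% / 44.7% | −3.8 |
| 60% / 90% | 43.8% / 40.9% | +2.8 |

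At 90% versus 80%, an assumed 12-week incidence of 20% gives −0.6 points and one of 60% gives −1.1.

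**Lower hazard off drug.** If the hazard halves after Week 12, I16 = 1 − 0.60 × 0.60^(0.5 × 4/12) = 44.9%. The excess over 12 weeks is 4.9 points instead of 9.4. The spurious difference becomes 0.1 × 4.9 = 0.5 points at 90/80 and 0.2 × 4.9 = 1.0 point at 90/70.

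**Withdrawal.** SAP 7 allows for up to 25% lost by Week 12. If that many withdraw equally in both arms, with equal windows, and the rollover shares apply to completers, the first set of differences shrinks to 0.75 × 0.94 = 0.7 and 0.75 × 1.88 = 1.4 points.

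Unequal withdrawal acts in the other direction. A subject observed only to Week 6 (assumed) has incidence 1 − 0.60^(6/12) = 22.5%, which is 17.5 points below 40%. Ten points more such withdrawal in one arm lowers its crude figure by 0.1 × 17.5, about 1.7 points. This can offset or reverse the rollover effect.

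**Against sampling error.** With 333 and 167 subjects and 40% incidence, the standard error of the difference is √[0.4 × 0.6 × (1/333 + 1/167)] = 4.6 points, a 95% half-width of about 9.

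**After the change.** With onset cut at Week 12 for all, completers give 40.0% in both arms at any rollover split. Events divided by time at risk gives h = 0.0426 per subject-week, whether a subject is observed for 6 weeks or 12.

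**The case against.** The strongest reply is that the SAP does what the protocol asks. Protocol 8.3.1 states that "All AEs will be collected from the time of signed informed consent until the final visit", and Protocol 10.4.3 summarises "AEs that occurred after administration of the first dose of study drug until completion of the final study visit". For a subject who rolls over, this study ends at Week 12 and later events belong to a separate study. Counting everything collected here is a defensible default. This stands: the rule is not a departure from the protocol, and replacing it would take post-treatment events, including serious ones, out of the main tables.

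Existing outputs also help. Each of the three AESIs gets a Kaplan-Meier figure of time to first event (SAP 12.9.1). Open-label enrolment and days in study are summarised by arm (SAP 12.1), as are days exposed (SAP 12.4). Adverse events are listed with onset dates. An imbalance would be visible. These outputs do not correct the percentages for any TEAE, serious TEAEs, or the SOC and preferred-term tables.

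A reader might infer that all subjects who do not roll over are followed for 16 weeks. The documents do not support that, because early withdrawers are in the same group. A reader might also infer that the arms are in fact compared over unequal windows, or that a safety difference could appear or vanish because of the rule. No rollover rate is given, so imbalance is only a possibility, and shifts of 1 to 2 points are small beside a standard error of 4.6.

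**Conclusion.** The point holds as a modest and conditional one. The rule makes counting time depend on a post-randomisation event, and no planned table removes that dependence for TEAEs in general. With assumed 40% incidence at 12 weeks and equal constant hazards, the distortion is about 1 point at 90% versus 80% rollover and 2 points at 90% versus 70%. It is about half that if the off-drug hazard is half, and none if rollover and follow-up are equal. Wider rollover gaps give more (3.8 points at 90% versus 50%). Differing withdrawal can change the sign. All of these rest on assumed rates. This is a cheap improvement to the reading of the safety tables; it does not make the planned summary invalid.

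**What to change.** Keep the protocol-defined summary to the final study visit and add the following to SAP 12.9.1 before unblinding.

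1. A supplementary TEAE summary with one cut-off rule for all subjects: onset from first dose to the earlier of the Week 12 visit and the subject's last contact. For a subject without a Week 12 visit, name a day to stand in for it, such as the Day 85 target in SAP 11.4. Show later events in a separate follow-up table, so that none is lost.
2. Exposure-adjusted incidence rates over that window for any TEAE, serious TEAEs and each AESI, with time at risk ending at the first event or the end of the window. This is needed because the common cut-off alone does not allow for early withdrawal.

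Reconcile the passages on whether early withdrawers also attend the Follow-Up Visit, so that last contact is well defined. The cost is some SAP wording and extra safety tables; no new data are needed. Exposure-adjusted rates assume a roughly constant hazard, so they belong beside the percentages and should not replace them.

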# SCHEDULE OF ASSESSMENTS

**Table 1:** Schedule of Assessments

	Screening	Baseline		Double-Blin	d Vehicle-Co	ontrolled Tro	eatment Phas	se	FU a	ETb
	V 1	V 2	V 3	V 4	P/C c	V 5	P/C c	V 6	V 7	NA
Procedures and Assessment	Day -34 to Day -1	Day 1	Week 2 D 15 (±2 d)	Week 4 D 29 (±2 d)	Week 6 D 43 (±2 d)	Week 8 D 57 (±2 d)	Week 10 D 71 (±2 d)	Week 12 D 85 (±2 d)	Week 16 D 113 (±4 d)	NA
Informed consent	X									
Demographics	X									
Medical history d	X	Xe								
Assess/confirm eligibility	X	X								
Serum/urine pregnancy test (WOCBP) f	X	X g		X		X		X	X	X
Brief physical examination	X h	X		X		X		X	X	X
Vital signs i	X	X	X	X		X		X	X	X
ECG	X									
Blood sample for clinical laboratory tests j	X			X				X	X	X
Urinalysis	X								X	X
HADS	X									
Subject randomization		X								
Photograph representative area of disease area k		X		X		X		X		
PK blood sample collection l				X				X		
Adverse events	X	X	X	X	X	X	X	X	X	X
Concomitant medication	X	X	X	X	X	X	X	X	X	X
Investigator Assessed:										
PGA score m	X	X	X	X		X		X	X	X
%BSA affected n	X	Xº	X	X		X		X	X	X
PASI		X	X	X		X		X	X	X
LTS p			X	X		X		X	X	X

	Screening	Baseline		Double-Blin	d Vehicle-Co	ontrolled Tre	eatment Pha	se	FU a	ETb
	V 1	V 2	V 3	V 4	P/C c	V 5	P/C c	V 6	V 7	NA
Procedures and Assessment	Day -34 to Day -1	Day 1	Week 2 D 15 (±2 d)	Week 4 D 29 (±2 d)	Week 6 D 43 (±2 d)	Week 8 D 57 (±2 d)	Week 10 D 71 (±2 d)	Week 12 D 85 (±2 d)	Week 16 D 113 (±4 d)	NA
Completed by Subject:										
DLQI		X		X				X	X	X
SF-36		X		X				X	X	X
PSD		X	X	X		X		X	X	X
LTS			X	X		X		X	X	X
Peak Pruritus NRS q		X	X	X	X	X	X	X	X	X
Dispense/collect diary r		D	C/D	C/D		C/D		С		С
Review subject diaries for treatment compliance			X	X		X		X		X
Dispense (D)/Collect (C) study drug		D	C/D	C/D		C/D		С		С
Review instructions for study drug application s		X	X	X	X	X	X			
Study drug application under supervision t		X	X	X		X				
Enrollment (optional) in long-term study					_			X	_	

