## 5.5. Treatment after the End of the Study

Subjects will not receive any additional treatment with the study drug from the Sponsor after completion of the study (with the exception of eligible subjects who enroll in the separate open-label, long-term study) because the indication being studied is not life threatening or seriously debilitating and other treatment options are available.

The Investigator is responsible for ensuring that consideration has been given to the poststudy care of the subject's medical condition, whether or not the Sponsor is providing specific poststudy drug.

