#### 7. TIMING OF PROCEDURES AND ASSESSMENTS

This section lists the procedures and assessment to be performed at scheduled timepoints during the study as outlined in the Schedule of Assessments (Table 1). Information on study procedures and assessment s is provided in Section 6.

- Any change in timing or any addition of a timepoint(s) for any planned study assessment must be documented in a "Note to File," which is approved by the relevant Sponsor study team member and then archived in the study Sponsor and site study files; this will NOT constitute a protocol amendment.
- The IRB/IEC will be informed of any safety issues that require alteration of the safety monitoring scheme or amendment of the Informed Consent Form (ICF).

NOTE: Assessments and procedures should be performed predose on clinic visit days.

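### If open-label tapinarof is first applied on the Week 12 date, the SAP's whole-day adverse-event cut-off would count later same-day events as double-blind events

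*SAP*

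**What the plan says.** SAP 12.9.1 separates two groups. For subjects who do not roll over, every reported adverse event (AE) goes into the double-blind summaries. For those who do, "all AEs with an onset date on or before the Week 12 visit date will be included in the Double-Blind phase summaries". The test is on the date, it is inclusive, and open-label dosing is not mentioned. The definition of treatment emergence sets a lower limit only: "A treatment-emergent AE (TEAE) is defined as an AE that starts after the first dose of study medication". The SAP revision history for Amendment 2 lists the inclusion of Week 12 onsets as a clarification, so the inclusive day is deliberate.

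Protocol 10.4.3 restricts the AE summaries to "AEs that occurred after administration of the first dose of study drug until completion of the final study visit". It also says: "Summaries of AEs will be presented separately for double-blind and open-label treatment phases". For a rollover subject the final visit is Week 12; SAP Section 9 defines the last study visit that way.

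The Schedule of Assessments (Protocol Table 1) has a row "Enrollment (optional) in long-term study", marked at Week 12. Protocol 5.5 rules out further study drug after completion, "with the exception of eligible subjects who enroll in the separate open-label, long-term study". Neither document gives the date or time of the first open-label application; Protocol 3.2 refers the reader to a separate protocol.

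The AE listing in SAP 12.9.1 will show, among other items, "onset date and time, end date and time, duration (days), CTCAE grade". Onset times are therefore expected to be available.

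**The concern.** Enrolment in the long-term study happens at the visit whose date is the cut-off. A date-only rule cannot tell an event that began before or during that visit from one that began after open-label cream was applied later the same day. For a subject randomised to tapinarof this hardly matters, because the product is the same. For a subject randomised to vehicle it would be a first exposure to tapinarof, and the event would be tabulated under vehicle.

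Any such misassignment would raise vehicle counts and narrow the apparent difference between arms. It would show most in the AEs of special interest (AESIs): contact dermatitis, folliculitis and headache. Each has its own detailed table and a Kaplan-Meier figure of time to first event, and for a single term one or two extra vehicle subjects could be visible.

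**Working it through.** The plan states no figure on this point, so there is none to reproduce. The check first traces one event through the rules and then bounds the number of such events.

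**Tracing an event.** Suppose a vehicle subject completes the Week 12 visit, enrols in the long-term study, applies open-label tapinarof that afternoon and has a headache that evening.

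| Question | Source | Answer |
|---|---|---|
| Onset date on or before the Week 12 date? | SAP 12.9.1 | Yes, included |
| Starts after first dose of study medication? | SAP 12.9.1 | Yes, treatment-emergent |
| Arm for tabulation? | SAP 8 (Safety population, as treated) | Vehicle |
| An AESI? | SAP 12.9.1 | Yes, headache |
| Before completion of the final study visit? | Protocol 10.4.3 | No, outside the window |

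The SAP includes the event and the protocol's window does not. Nothing else in SAP 12.9.1 removes it. SAP Section 13 does not list the wider window among the changes from the protocol.

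**Does the event arise?** Only if open-label drug is applied on the Week 12 date. Table 1 puts enrolment at that visit. Protocol 7.3.4 has double-blind drug collected there, and neither it nor Table 1 lists a supervised application. This makes same-day open-label dosing plausible but does not establish it.

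**Size, if it does.** Inputs:
- Vehicle arm: about 167 (SAP 7).
- Loss by Week 12: up to 25% (SAP 7), so completers = 167 × 0.75 = 125.25, about 125.
- Share of completers rolling over, r: not in the documents; assumed 50% to 100%.
- Probability that a rollover subject has an event starting that day after the application, q: not in the documents; assumed 0.5% to 1%.

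Expected vehicle subjects affected = 125.25 × r × q. Dividing by 167 gives percentage points of the vehicle arm.

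| r | q | Subjects | Points of 167 |
|---|---|---|---|
| 50% | 0.5% | 0.31 | 0.19 |
| 50% | 1% | 0.63 | 0.38 |
| 100% | 0.5% | 0.63 | 0.38 |
| 100% | 1% | 1.25 | 0.75 |

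The range is about 0.3 to 1.3 subjects. With no loss at all the top would be 167 × 0.01 = 1.7.

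As a deliberately extreme value, set q to 6%. That is the top of the range that Protocol 1.1.1 gives for the most frequent individual dermatological AEs in the early studies. The result is 125.25 × 0.06 = 7.5 subjects, or 4.5 points. But that 6% accrued over 28 to 84 days of treatment, so it is not a credible one-day rate.

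Two limits apply to every row. SAP 12.9.1 counts a subject once at each level of summary, so a vehicle subject with an earlier event at that level adds nothing; the points column is an upper limit on added incidence. The overlap is also at most the rest of one day in about 85: 1/85 = 1.2% of the window.

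**The case against.** The strongest objection is that the premise is missing. A reader might infer from enrolment at Week 12 that open-label reactions *are* being counted as vehicle events. The documents do not support that. Table 1 schedules enrolment, not an application, and marks supervised application only at the earlier visits. The general instruction "NOTE: Assessments and procedures should be performed predose on clinic visit days" says nothing about an open-label dose. The timing sits in a protocol that is not available here. This objection stands, and the point has to be conditional.

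Second, the inclusive day has a purpose: it keeps genuine double-blind events that began on the day of the visit. This also stands, and it is why the date should remain the outer limit.

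Third, an event after an open-label dose might be recorded only in the long-term study's database, since the SAP covers data from the double-blind phase. The documents do not settle this. The existence of a separate onset-date rule for rollover subjects suggests that events across the boundary were expected in the data, but that is an inference.

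Fourth, a reader might reach a larger effect, for example up to 4.5 subjects or 2.7 points, by taking 75% to 90% of all 167 vehicle subjects as rolling over and a same-day rate of up to 3%. The documents do not support this either. At the planned 25% loss, 75% of 167 is already every completer, so it is a ceiling and not a floor. The 3% has no source. Not every affected subject adds to incidence.

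Finally, safety data receive no formal comparison (SAP 12.9), so no test is at risk. That limits the severity, but the descriptive AESI tables and curves will still be read.

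**Conclusion.** The point holds in conditional form. The SAP's cut-off for rollover subjects is wider than the window in Protocol 10.4.3 and does not refer to open-label dosing. If the first open-label application is on the Week 12 date, events starting after it would enter the double-blind summaries, and a vehicle subject's first-exposure reaction would be tabulated under vehicle.

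The size is about 0.3 to 1.3 vehicle subjects. That rests on the planned 25% loss and on assumed ranges for rollover (50% to 100%) and same-day events (0.5% to 1%). The effect on incidence is smaller after once-per-subject counting, and it is zero if open-label dosing begins on a later day. A reader might conclude that the difference in harms is understated; the documents support only that it could be, slightly, under that condition. This is a cheap improvement of low severity.

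**What to change.** Keep the Week 12 visit date as the outer limit in SAP 12.9.1 and add to the rollover rule: *excluding AEs with onset (date and time) after the first open-label application on that date; an AE on that date with no recorded time is included only if it was recorded at the Week 12 visit assessments.* Apply the same cut-off to the AESI tables and the Kaplan-Meier figures.

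The outer limit matters. Cutting at the first open-label application alone would, if that dose came days later, admit every event in the gap and go beyond the protocol's window.

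The cost is one clause and a short derivation. AE onset time is already listed, but the time of first open-label application is not scheduled in this study and must be taken from the long-term study data. A few same-day events will need the fallback rule. If open-label dosing always starts on a later day, the clause changes nothing.

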#### 8.2. Classification of Adverse Events

#### 8.2.1. Assigning Severity Rating for Adverse Events

#### 8.2.1.1. Criteria for Determining Averse Event Severity

The Investigator will make an assessment of the severity of each AE and SAE according to the National Cancer Institute Common Terminology Criteria for Adverse Events (CTCAE), v. 5.0, 2017. For terms not specified with the CTCAE, the criteria in Table 4 should be used to determine the grade severity.

Table 4: Criteria for Determining the Grade/Severity of Adverse Event Terms Not Specified by the National Cancer Institute CTCAE

Grade	Criteria	
1	Mild; asymptomatic or mild symptoms, clinical or diagnostic observations only; intervention not indicated	
2	Moderate; minimal, local, or noninvasive intervention indicated; limiting age-appropriate instrumental activities of daily living a	
3	Severe or medically significant but not immediately life-threatening; hospitalization or prolongation of hospitalization indicated; disabling; limiting self-care activities of daily living b	
4	Life threatening consequences; urgent intervention indicated	
5	Death related to adverse event	

CTCAE = Common Terminology Criteria for Adverse Events.

- a Instrumental activities of daily living refer to preparing meals, shopping for groceries or clothes, using the telephone, managing money, etc.
- b Self-care activities of daily living refer to bathing, dressing and undressing, feeding self, using the toilet, taking medications, and not bedridden.

Adverse event severity should be recorded in the appropriate section of the adverse event case report form and in the subject's source documents.

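### SAP 12.9.1 imputes a missing AE severity to the top of the scale, and the top of the grading scale in this trial is death

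*SAP*

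**What the plan says.** **The imputation rule.** SAP section 12.9.1 states: "Missing severity will be imputed to the highest severity level (most severe"). It sets no upper limit, makes no exception for non-fatal events and provides no missing category.

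**The severity scale.** Protocol section 8.2.1.1 has the Investigator make an "assessment of the severity of each AE and SAE according to the National Cancer Institute Common Terminology Criteria for Adverse Events (CTCAE"), version 5.0. It adds: "For terms not specified with the CTCAE, the criteria in Table 4 should be used to determine the grade severity". Table 4 runs from Grade 1 to Grade 5, and Grade 5 is defined as "Death related to adverse event".

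**The tables that use the grade.** SAP section 12.9.1 plans a table of "All TEAEs by SOC, PT, and maximum CTCAE grade". Its subject-level rule is: "For summaries of TEAE CTCAE grade, a subject will be classified according to the worst grade". For AESIs with more than one occurrence in a subject, the "highest levels of causality and seriousness, maximum grade and generally the most extreme level of each characteristic will be summarized".

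**Fatality recorded elsewhere.** Protocol section 8.3.2 has the Investigator record an outcome for each AE, with Fatal as one option. SAP section 12.9.1 includes outcome in the AE listing and plans a Death row in the overall AE summary.

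**The concern.** Worst-case imputation of severity suits a mild/moderate/severe scale, where the top category is still a degree of intensity. Here the top category is an outcome. Assigning it to an event in a living subject does not err on the cautious side; it contradicts another field in the same record.

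The companion rule in 12.9.1, which treats a missing causality as related to study drug, does not have this problem, because no other recorded field shows it to be false.

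The stake is the coherence of the safety tables in a study that protocol section 1.1.2 describes as pivotal and intended to support US registration. If a grade is missing at lock, the programmer must either produce a Grade 5 entry that did not occur or depart from the SAP with an unwritten cap, possibly after unblinding.

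**Working it through.** The plan gives no figure of its own here, so the check sets the text side by side and then works out the size per subject.

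1. **What severity means in the SAP.** The AE listing in 12.9.1 carries CTCAE grade and no other AE severity field. The severity table is by maximum CTCAE grade. Where 12.9.1 says that TEAE severity will be summarised, the rule that follows is stated in grades. The imputation sentence therefore acts on CTCAE grade.

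2. **The value it gives.** On the scale in Table 4, imputed grade = max{1, 2, 3, 4, 5} = 5, which is death. The highest non-fatal level is Grade 4, "Life threatening consequences; urgent intervention indicated".

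3. **How it carries forward.** Subject grade = the maximum over that subject's events at the level being summarised. Take, for illustration, a subject with a Grade 1 event, a Grade 2 event and one ungraded non-fatal event, all in the same SOC. With imputation the SOC-level grade is max{1, 2, 5} = 5; from the recorded grades alone it is max{1, 2} = 2. The ungraded event is also Grade 5 at its own PT. If it is an AESI, the AESI summary inherits the value through its maximum-grade rule.

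4. **Whether another section corrects it.** SAP section 9 gives rules for missing AE dates and missing efficacy data. It closes by saying that missing safety endpoints are not imputed. It does not mention AE grade, cap the rule in 12.9.1 or link it to outcome.

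5. **Size per affected subject.** Denominators are the planned arm sizes in SAP section 7, about 333 and 167. The Safety population requires at least one application, so actual denominators may differ.
   - Tapinarof: 1/333 = 0.0030, about 0.3%.
   - Vehicle: 1/167 = 0.0060, about 0.6%.

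6. **Effect of 2:1 allocation.** If ungraded events are equally frequent per subject in both arms, two affected tapinarof subjects correspond to one on vehicle: 2/333 = 0.6% and 1/167 = 0.6%. The counts differ but the percentages do not.

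The total effect is the number of affected subjects times the step-5 figure. The documents do not give that number.

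**The case against.** **The wording may have meant Severe.** The sentence speaks of a severity level rather than a grade, and protocol section 8.1.3 has sites collect mild/moderate/severe for the three AESIs. In Table 4, Severe is the label of Grade 3. This reading does not fit: Grade 3 is the third of five levels, not the highest, and the SAP's AE tables use CTCAE grade. The mild/moderate/severe wording belongs to descriptive AESI detail.

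**Section 9 could be read as overriding the rule,** because it leaves missing safety endpoints unimputed. But 12.9.1 is the specific instruction, and grade is an attribute of an event rather than a listed safety endpoint. At most the two sections sit awkwardly together.

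**The rule may never be used.** Protocol sections 8.2.1.1 and 8.2.2 require severity to be recorded and AEs to be fully documented. Protocol sections 9 and 11.3.1 provide for queries and monitoring for completeness, and SAP section 5 puts lock after data review. This stands as a limit on frequency. It does not make the rule right when it is used.

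**The CTCAE scale itself is not reproduced.** This also stands. The documents define Grade 5 as death only in Table 4, for terms that CTCAE does not specify. A reader might infer that an ungraded headache or folliculitis must become a fatal-grade entry. The documents do not show the top grade for those terms, nor whether the SAP's highest level is meant term by term.

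**A misfire would be visible.** The listing shows grade, outcome and seriousness together, and 12.9.1 does not say that the Death row comes from grade. This stands too: the harm is an inconsistency between tables, not a concealed error.

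**Conclusion.** The rule in SAP 12.9.1 is wrong for the scale it is applied to. Read literally, it puts a non-fatal ungraded TEAE or AESI in a fatal grade at PT and SOC level and in the AESI maximum-grade summary. The size is about 0.3 percentage points per affected tapinarof subject and 0.6 per affected vehicle subject, on planned arm sizes. It rests on two conditions: at least one grade is missing at lock, and the top grade for that term is death, as in Table 4.

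Four stronger conclusions might be inferred and are not supported:

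- **A total number of false fatal-grade events.** This would need an AE count and a missing rate that the documents do not give.
- **A bias against tapinarof from its larger arm.** Equal missingness per subject gives equal expected percentages.
- **An inflated death count.** Outcome is recorded separately, and no text derives the Death row from grade.
- **Distortion of an overall any-TEAE row by grade.** The grade table is specified by SOC and PT only.

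No formal safety comparison is planned, and efficacy, power and alpha are unaffected. It is worth correcting because the error is clear and the repair is small.

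**What to change.** Replace the severity sentence in SAP 12.9.1 with:

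*A CTCAE grade still missing after query will be shown in a separate Missing category in the TEAE and AESI grade summaries; Grade 5 will be used only when the recorded AE outcome is fatal.*

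If the sponsor prefers to keep a worst-case imputation, cap it at the highest non-fatal grade unless the recorded outcome is fatal. The documents give no basis for choosing a particular lower grade as the default. The Missing category is the simpler option and also sits better with the closing statement of SAP section 9.

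The cost is one sentence, a small programming change and one extra row in the grade tables. No new data are needed. The change should be made before database lock and unblinding.
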